Under the same model described for SNS success, adverse events will be monitored assuming an *a priori* probability of limiting adverse events following Beta(0.6, 1.4) in the current patient cohort. Cohort limiting events (CLE) are defined as perioperative cardiovascular events, readmission if it is related to the SNS procedure, SNS lead removal due to any reason other than failure, or perioperative death due to surgery or complications. The patient cohort will be terminated if $\text{Prob}(\text{CLE} > 0.30 | \text{data}) > 0.95$. The specific rules for stopping after each cohort are included in the table here.

If there are this many patients (or more) with CLE	5	7	9	12	14
Stop the patient cohort if there are this many (or fewer) patients who are evaluable (have CLE, had battery implant without CLE, or had leads removed for failure without CLE.)	6	12	18	24	30*

* The cohort will stop at 30 patients, but if 14 or more patients have CLE, then the implant is too dangerous for this cohort.

Six patients will be accrued before the first analysis. If 5 or more of the 6 patients have CLE, stop the cohort and the implant will be declared as too dangerous for this population. If there are 4 or fewer CLEs, enroll the next 6 patients assuming the cohort didn't stop for futility.

The operating characteristics are summarized in the following table:

The operating characteristics for each patient cohort are shown in the following table.

		Stop if $\text{Prob}\{\theta_S < 0.50 \text{data}\} > 0.95$ or Stop if $\text{Prob}\{\text{CLE} > 0.30 \text{data}\} > 0.95$	
True	True	Pr(stop early)	Mean Number of Median

Adverse Event Rate	Response Rate		Patients	(25 th %ile, 75 th %ile)
0.1	0.30	0.68	18.5	12 (12, 30)
0.2	0.30	0.68	18.5	12 (12, 30)
0.3	0.30	0.71	18.0	12 (12, 30)
0.4	0.30	0.79	16.5	12 (12, 24)
0.5	0.30	0.90	14.0	12 (12, 18)
0.1	0.40	0.33	24.6	30 (18, 30)
0.2	0.40	0.33	24.5	30 (18, 30)
0.3	0.40	0.38	23.7	30 (12, 30)
0.4	0.40	0.55	21.0	18 (12, 30)
0.5	0.40	0.79	16.8	12 (12, 24)
0.1	0.50	0.10	28.3	30 (30, 30)
0.2	0.50	0.11	28.1	30 (30, 30)
0.3	0.50	0.18	27.1	30 (30, 30)
0.4	0.50	0.40	23.7	30 (18, 30)
0.5	0.50	0.72	18.4	18 (12, 30)
0.1	0.60	0.02	29.6	30 (30, 30)
0.2	0.60	0.03	29.5	30 (30, 30)
0.3	0.60	0.10	28.4	30 (30, 30)
0.4	0.60	0.34	24.7	30 (18, 30)
0.5	0.60	0.69	19.0	18 (12, 30)
0.1	0.70	0.003	30.0	30 (30, 30)
0.2	0.70	0.01	29.8	30 (30, 30)
0.3	0.70	0.08	28.7	30 (30, 30)
0.4	0.70	0.33	25.0	30 (18, 30)
0.5	0.70	0.68	19.1	18 (12, 30)

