7. RISK MANAGEMENT

Restore is a low risk trial. Any of the risks encountered by the participant are those associated with surgery for the treatment of fecal incontinence or LARS. In the event that readmissions or SNS lead removals are high, the study will be terminated as described in the previous section. We feel that any risk associated with participation in *Restore* is minimal and will be offset by improved patient reported outcomes. The knowledge obtained by the study personnel regarding the feasibility of sacral nerve stimulation for the treatment of fecal incontinence and LARS in association with colorectal cancer will be used to assess the potential of expanded cohorts as previously described. Adverse events (AE), \geq grade 3, using CTCAE v. 4 and serious adverse events (SAE) related to the procedure that occur within 30 days after will be reported. Reportable AE and SAE would include, but are not limited to, lead migration, wound infection, pneumonia, intractable pain related to surgical complications such as wound infection, unplanned or unanticipated readmission within 30 days, stroke, myocardial infarction, perioperative cardiovascular events, readmission if it is related to the SNS procedure, SNS lead removal due to any reason other than failure, or perioperative death due to surgery or complications.

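### Section 6.5 attaches no pause or review to a perioperative death: unless futility stops the cohort, one to four deaths in the first six still lead to the next six being enrolled

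*Combined protocol and SAP*

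**What the plan says.** The safety part of section 6.5 defines a single composite: "Cohort limiting events (CLE) are defined as perioperative cardiovascular events, readmission if it is related to the SNS procedure", then lead removal for any reason other than failure, "or perioperative death due to surgery or complications". A patient with any one of these counts once, and the type of event plays no part in the rule.

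The prior is stated as "limiting adverse events following Beta(0.6, 1.4) in the current patient cohort", and a cohort stops when the posterior probability that the CLE rate exceeds 0.30 is above 0.95. The boundaries are 5, 7, 9, 12 and 14 patients with a CLE among 6, 12, 18, 24 and 30. For the first look this is spelled out in both directions: "If 5 or more of the 6 patients have CLE, stop the cohort", and otherwise "If there are 4 or fewer CLEs, enroll the next 6 patients assuming the cohort didn't stop for futility". At 30 patients, "if 14 or more patients have CLE, then the implant is too dangerous for this cohort".

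The futility part of 6.5 runs alongside and stops a cohort at 0, 3, 5 or 7 successes or fewer at the first four looks. Accrual is held for evaluation after each group of six, separately by cohort.

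Section 7 opens with "Restore is a low risk trial". It lists perioperative death among the events to be reported. Its sentence on terminating the study names readmissions and lead removals, and refers back to section 6.

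**The concern.** A 30% limit may be tolerable for readmission or lead removal. Because the events are pooled, it is also the only numerical limit on death. Between looks, and at any look with four or fewer CLEs in six, the written instruction after a death is the same as after a readmission: carry on enrolling.

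This is elective outpatient surgery to improve function. In the radiation-only cohort, section 2 says that there are no published data on the device, and section 6.1 gives establishing safety as a purpose. If a death occurred, a pause would have to come from somewhere other than section 6.5, and against its explicit instruction to enrol.

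**Working it through.** **Inputs (section 6.5).** Prior Beta(0.6, 1.4); limit 0.30; cut-off 0.95; looks at 6, 12, 18, 24 and 30; safety boundaries 5, 7, 9, 12, 14; futility boundaries 0, 3, 5, 7, 10 with a Beta(1, 1) prior and limit 0.50. The documents give no expected or acceptable death rate, so the death rates below are assumptions.

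**1. The plan's own figures.** With x CLEs in n patients the posterior is Beta(0.6 + x, 1.4 + n − x). The boundary is the smallest x for which P(rate > 0.30) exceeds 0.95.

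| n | Largest x that continues (probability) | Smallest x that stops (probability) |
|---|---|---|
| 6 | 4 (0.945) | 5 (0.991) |
| 12 | 6 (0.905) | 7 (0.969) |
| 18 | 8 (0.883) | 9 (0.951) |
| 24 | 11 (0.938) | 12 (0.974) |
| 30 | 13 (0.929) | 14 (0.967) |

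All five safety boundaries reproduce, as do the five futility boundaries. All 25 early-stopping probabilities in the operating-characteristics table reproduce to within 0.006.

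**2. First look.** Four CLEs in six give Beta(4.6, 3.4), with mean 4.6/8 = 0.575 and P(rate > 0.30) = 0.945. The rule continues, whether the four events are readmissions or deaths. It therefore also continues after one, two or three deaths, provided no more than four patients have any CLE. Futility stops the cohort only at 0 successes in 6. If four patients died before implantation, one success among the other two would be enough to continue.

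**3. Safety rule alone, deaths as the only CLEs.** At a true death rate d, P(5 or more in 6) = 6d⁵(1 − d) + d⁶. For d = 0.10 this is 0.000054 + 0.000001 = 0.000055; for d = 0.20 it is 0.001536 + 0.000064 = 0.0016. Exact enumeration over the looks at 6, 12, 18 and 24 gives:

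| True death rate | Deaths expected in 30 | P(stop early) |
|---|---|---|
| 5% | 1.5 | 0.000002 |
| 10% | 3 | 0.0001 |
| 20% | 6 | 0.008 |
| 25% | 7.5 | 0.030 |

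**4. Both rules together.** Section 6.3 defines success as battery implantation at visit 3, so a death before implantation counts as a non-success. Let s be the success rate among survivors and suppose every death precedes implantation. Each patient then dies with probability d, succeeds with probability (1 − d)s, or does neither. Exact enumeration of both rules gives P(stop early):

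| s | No deaths | d = 10% | d = 20% |
|---|---|---|---|
| 50% | 0.10 | 0.19 | 0.33 |
| 60% | 0.02 | 0.06 | 0.14 |
| 70% | 0.002 | 0.011 | 0.045 |

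A rough cross-check is available in the plan. At d = 20% and s = 50% the success rate is 0.80 × 0.50 = 0.40, and its table gives 0.33 for a response rate of 0.40 with a 20% adverse event rate. If s is 79%, close to the permanent implantation rate that section 2 cites from a systematic review, the figures at d = 10% and 20% are about 0.002 and 0.017.

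Deaths after implantation would not feed the futility rule: those patients have already counted as successes.

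**The case against.** Pooling events into one composite is a legitimate monitoring design, and this one performs as its authors say. No passage contradicts another, and a reader who inferred that the safety table is miscalculated would be wrong.

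A reader might also infer that the plan ignores deaths altogether. It does not: section 7 makes a perioperative death reportable, section 6.6 has CLEs tabulated, and 6.5 says in general terms that a cohort continues if adverse event rates are reasonable. What none of these does is attach a pause or review to a death. One block of text was removed before this review, so any oversight wording there could not be checked. Institutional oversight might well step in, but the supplied text does not say so.

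A third tempting reading is that a cohort with high mortality would almost surely run to 30. That rests on the safety rule alone. With futility included the chance of stopping early can reach 0.33, although much of that reflects modest efficacy: it is already 0.10 with no deaths when 50% succeed.

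Finally, four deaths in six is remote, with probability 0.0013 at a true death rate of 10% and about 0.00009 at 5%. That stands. The scenario shows where the written limit lies; the practical case is one or two deaths, where the instruction is the same.

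**Conclusion.** The point holds as a gap in the design, not as an error. Section 6.5 responds to a perioperative death only through an equally weighted composite with a 30% limit. Unless futility stops the cohort, one to four deaths in the first six lead to six more patients being enrolled.

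The safety rule alone gives early stopping of 0.0001 and 0.008 at true death rates of 10% and 20%, if deaths are the only CLEs; other CLEs would raise these figures. With both rules and all deaths before implantation the range over 50% to 70% success among survivors is 0.19 down to 0.011 at a 10% death rate, and 0.33 down to 0.045 at 20%. The futility rule is thus weakest as a backstop when the device works well, and gives none for deaths after implantation.

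The documents do not support saying that the sponsor accepts 30% mortality, or that such death rates are expected. They state no acceptable death rate, and none is proposed here.

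**What to change.** Leave the CLE definition, its boundaries and the operating characteristics as they are. Add one sentence to section 6.5: any perioperative death holds accrual to that cohort until the sponsor's existing safety oversight has reviewed the death and released the hold. The supplied text does not describe that oversight, so the sentence should say which body it is. Also tabulate CLEs by component at each look, so that a count of four shows what the four events were.

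No new numerical boundary is needed. A separate count for cardiovascular events is not recommended, since it would be a further stopping rule needing its own operating characteristics.

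The cost is a possible short pause in a trial that already holds accrual after every six patients. It would seldom be used if deaths are rare: at an assumed death rate of 1%, the chance of at least one death in six patients is 1 − 0.99⁶ = 0.059.

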6.6. Analysis Plan

The proportion of patients who experience SNS success will be reported with a 90% credible interval using a beta(1,1) prior for each cohort. For the patients in the reconstruction cohort, a success rate of 50% or better will establish confirmation of efficacy of SNS implant that would warrant offering SNS implant to alleviate bowel symptoms following anal reconstruction. In the chemoradiation therapy only cohort, a success rate of 50% or better would warrant studying SNS implant further in this patient population. The secondary measures will be reported descriptively with graphs or tabulations for categorical survey outcomes, CLEs, and anorectal manometry measures. Exploratory logistic regression models will be performed to identify patients who may be more likely to have SNS success using baseline measures and visit 2 bowel/bladder diaries. Analysis of SNS success, safety, and measures up through visit 4 measures will be completed and published once all patients are enrolled and complete the first 4 visits or are off study. Additional analyses will be completed and published after the long-term 1 and 3 year follow-up questionnaires are completed.

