Rationale: FI and LARS are often debilitating and recalcitrant to current medical therapies including medicinal and biofeedback. A recent systematic review of the literature for patients with FI or LARS and who underwent SNS placement following chemoradiation and surgery for rectal cancer reported data on 42 patients from 7 articles with promising results. Ramage *et al* reported an overall permanent implantation rate of 79.1% with the lowest reported at 47%. [25] The efficacy of SNS in these few patients revealed significant decrease in nocturnal defecation from 3 (pre-SNS) to 0.5 (post-SNS) episodes/night, decrease in incontinence from 7 (pre-SNS) to 0.2 (post-SNS) episodes/day episodes, and 67% of patients reported complete resolution of LARS (fragmented defecation, urgency, or soiling). [25] The majority of literature specifically excluded patients with cancer and although reported in 42 patients following rectal cancer treatment (chemoradiation and surgery), this study aims to prospectively evaluate the efficacy of SNS placement in cancer patients who have undergone pelvic combined chemoradiation therapy for their rectal cancer treatment followed by a restorative proctectomy with either a low colorectal or coloanal anastomosis who exhibit subsequent significant, debilitating FI or LARS with or without urinary symptomatology. Additionally, we aim to assess the feasibility of SNS placement in patients who have developed FI or defecatory dysfunction (including urgency and leakage) following radiation treatment without surgery for cancers including anus, prostate, uterus, cervix, vagina, and vulva as this has not been reported.

The results of this study will be useful in the management of patients with bowel dysfunction either from FI or LARS following restorative rectal cancer surgery expanding available treatment alternatives including SNS. Future directions from this study include expansion of the patient population for a phase 2 trial and include an efficacy arm for patients treated with pelvic radiation without surgery including anal, gynecologic and urological malignancies.

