5. STUDY METHODS

Patient Selection

Both study cohorts will be evaluated and managed at the same. Total accrual to this study is 66 patients for enrollment of 60 evaluable patients to the study, 30 patients into each cohort, at the UT MD Anderson Cancer Center (UTMDACC) in Sugar Land, Texas. Patients meeting study eligibility will be screened prospectively in relevant UTMDACC clinics, which are a likely source of patients to be identified for screening, or through physician referral to the study.

Study Enrollment

All patients will undergo a complete history and physical, per routine standard of care. Patients disclosing FI or LARS will sign consent and be pre-registered on the study in CORe for screening and will complete questionnaires (on paper, over the phone/teleconference system, or electronically through REDCap) related to general quality of life, FI severity, and LARS.

Patients may access the questionnaires electronically in the REDCap system via a link sent to them by email or MyChart (Appendix K). Patients will then undergo an anorectal manometry for pelvic pressure readings per standard of care. Then, patients who disclose appropriate bowel dysfunction (urgency, alternating diarrhea and constipation, fragmentation, obstructive defecation, and stacking) and with abnormal anorectal manometry readings and questionnaire responses indicating study eligibility, will proceed with enrollment in the study. Patients who are found not to meet eligibility based on bowel dysfunction reporting, questionnaire responses and anorectal manometry results will be removed from the study. Patients meeting all eligibility criteria with insurance pre-authorization for all procedures will be enrolled on the study.

Patients on-study with lab results described below before SNS placement will be given 30 days to improve and will be re-evaluated. Patients will have these tests ordered for routine standard of care based on the determination of the physician. If no improvement at 30 days, patients will be taken off study, data collected up to this point may be used in study reporting.

- ANC <1.7, INR >1.3, platelet count <50K

On-study patients requiring systemic therapy for an infection before SNS placement will be given 30 days to improve and will be re-evaluated. If no improvement at 30 days, patients will be taken off study, data collected up to this point may be used in study reporting.

Procedure to Obtain Informed Consent

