8. International Consultation on Incontinence Questionnaire-Female Lower Urinary Tract Symptoms (ICIS-FLUTS) if female and International Continence Society Male Short Form (ICSmaleSF) if male: Validated instruments to measure urinary dysfunction.
9. Low Anterior Resection Syndrome (LARS) Bowel Function Questionnaire: This is a validated instrument, to be provided only to the restorative surgery cohort, designed to assess clinical severity of symptoms of LARS outside of just FI and will be a significant tool to address extending criteria for SNS use outside of FI.
10. EORTC QLQ-CR29: this is a quality of life instrument validated for patients with colorectal cancer. This will be provided to all patients.

Study Visits

Initial Evaluation/Visit 1: Patients are referred to the clinic for reported refractory FI or LARS. Upon arrival to their initial clinic visit, the patients will complete the validated questionnaires and instruments (on paper, over the phone/teleconference system, or electronically through REDCap), as well as an ARM. A minimum score from the FISI will not be required as this was not required for the initial studies in the benign disease patients, though it is anticipated that their scores will be around a score of 30, a number defined as what is typical for patients who have a significant quality of life impairment due to their reported fecal incontinence. The results will then be reviewed for appropriateness to be considered eligible for the study. Patients will sign consent and then be enrolled after appropriate evaluation by the clinical and research teams and all inclusion and exclusion criteria are met. The remaining questionnaires will be completed and a complete review of symptoms and physical exam will be performed per standard of care. A post-void residual bladder scan will be performed at this visit after enrollment as well. After all objective data are collected, each patient will be scheduled for surgery for placement of a sacral nerve stimulator under general anesthesia in the operating room as per standard of care. All patients are asked to begin recording all daily bowel and bladder habits in the bowel and bladder

trackers to serve as their baseline function. Necessary preoperative testing will be ordered and completed at UTMDACC including appropriate consultant visits as per standard of care for any operation.

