6.3. Endpoints

Primary Endpoints

The primary endpoint is SNS Success. *SNS Success* will be measured as a patient having the battery implanted at visit 3 which can only happen if they've achieved improvement in fecal incontinence at visit 3. Patients who do not have the SNS placed, for any reason other than insurance coverage issues, will count as not having a success.

Fecal incontinence will be measured by the physician as the total number of gas, mucus, liquid stool, and solid stool accidental leakage events reported in the bowel diaries.

Improvement will be determined by the physician based on bowel diary comparisons recorded before SNS lead placement at visit 1 to after lead placement at visit 2. This is done at visit 3 when the patient presents for consideration of placement of the implantable battery. Any patient who comes in for SNS placement but the SNS cannot be successfully placed for any reason other than insurance reasons will count as not having improvement. Patients meeting this improvement will have their *battery implanted*. Patients will be counted as having their battery implanted if it is implanted at Visit 3 if they had the SNS placed at Visit 2.

Secondary Endpoints

- **FISI** overall questionnaire summary
- **FIQOL** overall questionnaire summary
- **ARM** score
- **EQ-5D-5L**
- **ICSmaleSF** or **ICIS-FLUTS** (females)
- **MSKCC BFQ (for restorative surgery cohort)**
- **LARS Score Bowel Function Questionnaire (for restorative surgery cohort)**

- **CCIS (for radiation only cohort)**
- **Bowel Diaries**
- **Bladder Diaries**
- **EORTC QLQ-CR29**
- **FISI, FIQOL, EQ-5D-5L, ICSmaleSF or ICIS-FLUTS, MSKCC, EORTC QLQ-CR29 and CCIS will also be collected at 1 and 3 years for long-term evaluation.**

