6.4. Sample Size

Up to 30 patients will be entered in each cohort, monitored after every 6 patients according to the interim analyses plans below. The selection of 30 patients per cohort combines feasibility of accrual and operating characteristics of the decision rules. If a cohort accrues to full size and has a 50% SNS success rate (15/30) then the 90% credible interval using a prior of beta(1,1) would be (35.7%, 64.3%). Patients who complete baseline measures and sign consent but who are not able to undergo SNS implant for insurance issues will not be evaluable for this study. Accrual numbers have been inflated by 10% to allow for unevaluable patients taken off study for a total study enrollment of up to 66 patients to have an evaluable 60 patients.

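### Section 6.6 sets no limit on predictors, no shrinkage and no validation for its responder models, and it names as a predictor the visit 2 bowel diary that helps to decide the outcome

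*Combined protocol and SAP*

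**What the plan says.** The plan for these models is one sentence in Section 6.6: "Exploratory logistic regression models will be performed to identify patients who may be more likely to have SNS success using baseline measures". The sentence continues, so that the full predictor specification is "using baseline measures and visit 2 bowel/bladder diaries". The section does not list predictors or cap their number. It does not say whether the models are univariable or multivariable, ordinary or penalised, per cohort or pooled. It gives no selection rule and no internal validation.

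On the available data, Section 6.4 says "Up to 30 patients will be entered in each cohort". Section 5 gives the total: "Total accrual to this study is 66 patients for enrollment of 60 evaluable patients to the study, 30 patients into each cohort". Section 2 cites, for patients after chemoradiation and surgery for rectal cancer, an "overall permanent implantation rate of 79.1% with the lowest reported at 47"%.

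On candidate predictors, Section 5 says that at the first visit "the patients will complete the validated questionnaires and instruments", together with manometry. Section 6.3 reduces FISI and FIQoL to an "overall questionnaire summary" each, but does not say which scores of the other instruments would be modelled.

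On the outcome, Section 6.3 defines success as battery implantation at visit 3. The physician decides this by comparing the bowel diary from before lead placement with the one from after it. Section 5 (Visit 3) applies a threshold of a 50% decrease. A patient in whom the stimulator is not placed counts as a failure, unless insurance is the reason.

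**The concern.** A logistic model with many predictors and few patients in the smaller outcome group fits the accidents of the sample. Its apparent discrimination is then high even when no predictor carries information, and its odds ratios are too far from 1 or have no finite estimate. Nothing in Section 6.6 prevents this.

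The second problem does not depend on sample size. A predictor that forms half of the comparison deciding the outcome will look strong whether or not anything measured before treatment predicts response. At stake is the stated purpose of the models, to identify patients more likely to succeed. A published model could suggest that such patients can be recognised when the data do not show it.

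**Working it through.** **The plan's own figure.** Section 6.4 gives a 90% credible interval for 15 of 30 successes under a beta(1,1) prior. The posterior is Beta(1 + 15, 1 + 15) = Beta(16, 16). Its 5th and 95th percentiles are 35.66% and 64.34%, which match the stated 35.7% and 64.3%. The plan gives no figure for the logistic models.

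**Smaller outcome group** = n × min(rate, 1 − rate).

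- Per cohort at 50% success: 30 × 0.50 = 15.
- Per cohort at 79.1%: 30 × 0.209 = 6.3, about 6.
- Pooled, n = 60: 60 × 0.50 = 30; at 80%, 60 × 0.20 = 12.

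The 79.1% applies to the restorative surgery cohort only. Section 2 says that no data exist on SNS after radiation without surgery, so a smaller group of 6 is only an assumption for the radiation only cohort. Nor is 6 a floor: under Section 6.5 a cohort that stops at 12 patients with 3 or fewer successes has at most 3 in the smaller group.

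**Candidate baseline measures**, counted from Section 5.

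- Restorative surgery cohort: 7 questionnaires (FIQoL, FISI, EQ-5D-5L, MSKCC, LARS, CR29, urinary), manometry, post-void residual, bowel diary and bladder diary, so 11.
- Radiation only cohort: CCIS replaces MSKCC and LARS, so 10.
- Subscales and the open-ended clinical data would add more.

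With 10 predictors there are 6/10 = 0.6 to 15/10 = 1.5 smaller-group patients per predictor.

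**Noise simulation.** Predictors are independent standard normal and unrelated to outcome. The model is an unpenalised maximum-likelihood logistic fit, with 1,500 data sets per setting. The AUC on fresh data was 0.50 throughout. For one cohort of 30:

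| Predictors in model | Mean apparent AUC, smaller group 15 | AUC ≥ 0.70 | Perfect separation | Mean apparent AUC, smaller group 6 | AUC ≥ 0.70 | Perfect separation |
|---|---|---|---|---|---|---|
| 1 | 0.58 | 6% | 0% | 0.60 | 14% | 0% |
| 2 | 0.63 | 17% | 0% | 0.67 | 35% | 0% |
| 5 | 0.73 | 63% | 0% | 0.78 | 81% | 1% |
| 10 | 0.84 | 97% | 5% | 0.92 | 99% | 40% |

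Repeat runs gave 0.72 and 0.85 for 5 and 10 predictors with 15 in the smaller group, so the means are good to about 0.01. Pooled (n = 60, smaller group 30 to 12), 10 predictors give 0.73 to 0.78 and 5 give 0.66 to 0.70.

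**Bias of the odds ratio.** With two predictors and a true log-odds ratio of 0.7, maximum likelihood averaged 0.82 to 0.97 at these sizes. Firth fitting averaged 0.69 to 0.72, with lower error.

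**Visit 2 diary.** Let B and V be the leakage counts before and after lead placement. A 50% decrease means V ≤ 0.5 × B, that is, V − 0.5B ≤ 0. This is a straight line in B and V. If the rule is applied exactly, a model holding both counts separates successes from failures perfectly: the AUC is 1.00 and there is no finite maximum-likelihood estimate. V alone gave an AUC of about 0.88 under an assumed distribution (over-dispersed baseline counts, log-normal ratio of V to B with median 0.5 and log-scale SD 0.7). That 0.88 is illustrative, because the documents give no diary distribution. In addition, a failure with no stimulator placed has no post-placement diary and drops out of any complete-case model that uses it.

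**The case against.** A reader might infer that the plan fits ordinary regression to many measures and so would report noise as prediction. The documents do not support that. Section 6.6 names only exploratory logistic models. The analyst could fit one or two predictors at a time, pool the cohorts, or penalise. With one or two predictors the noise AUC is modest, and pooling raises the smaller group to about 12 to 30. This stands: the defect is missing specification, and the large figures hold only if several measures enter one ordinary model. Pooling is not a full answer, because MSKCC and LARS are given to one cohort only and CCIS to the other.

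A reader might also infer that finite estimates would often be missing. Separation was common (40%) only with 6 patients and 10 predictors.

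Under one-at-a-time screening, ten independent tests at 0.05 give 1 − 0.95^10 = 0.40 for at least one false signal. But the plan sets no significance threshold and the questionnaires overlap. Even under independence the simulated figure was 26% to 29% with Wald tests and 44% to 48% with likelihood-ratio tests. The 40% should not be presented as a property of the plan.

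Last, a reader might infer that the models will govern patient selection in later trials. No section says so. Section 6.6 rests both cohort conclusions on the 50% success rate, and Section 2 describes future work as expanding the population. The exploratory label is fair and keeps the point minor. It does not remove optimism from a reported AUC, or the overlap between the visit 2 diary and the outcome.

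**Conclusion.** The point holds as under-specification plus one definite overlap. Section 6.6 leaves the predictors, fitting and validation open where a cohort offers about 6 to 15 patients in the smaller outcome group. If 5 to 10 measures enter one ordinary model per cohort, the apparent AUC on noise is about 0.72 to 0.92. With one or two predictors it is 0.58 to 0.67, so a cap removes most of the problem and validation is needed for the rest. These sizes assume a full cohort of 30, success between 50% and about 79%, and independent normal predictors.

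The visit 2 bowel diary finding needs no simulation: Section 6.3 uses that diary to decide success. The overlap is partial rather than total, because the physician makes the judgement, Section 5 also counts LARS symptoms, and patients never implanted with leads fail without a diary.

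Neither part touches the primary analysis, the stopping rules or the sample size. Severity is low.

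**What to change.** Amend the sentence in Section 6.6 to:

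- State whether the models are per cohort or pooled.
- Name at most two baseline predictors per model in advance, and the score used for each. Baseline FISI is a natural candidate, since Section 5 requires no minimum score. Resting pressure and maximal tolerance are less informative, because Section 3 restricts both by eligibility.
- Drop the visit 2 bowel diary as a predictor.
- Fit with Firth-penalised logistic regression.
- Report odds ratios with intervals and a bootstrap optimism-corrected AUC, and label the results hypothesis-generating. With about 6 in the smaller group the corrected AUC will itself be imprecise, and the report should say so.
- Tabulate all other measures by outcome.

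The cost is SAP wording only, with no added patients, visits or data. The small downside is that fewer measures are modelled together.
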